10.6 Interim Analysis

Prior to the interim analysis, two administrative analyses will be performed on available safety and immunogenicity data collected during the 14 days after each vaccination; Administrative

Analysis #1 will include Group A, B and C data for Days 0-28; Administrative Analysis #2 will include safety and immunogenicity data for Days 28-42.

The final interim analysis will include data from the preceding administrative analyses (#1 and #2) as well as all new data through Day 56. This analysis, regarding to safety and immunogenicity of A, B and C groups, will be implemented after subjects with two vaccinations in A group, B group and C group have completed Visit 9 (Day 56), which is 28 days after 2nd vaccination. Interim analysis population will be the subjects in groups A, B and C who had completed two vaccinations. For the evaluation of safety and immunogenicity, the following endpoints will be included in the interim report.

- Occurrence of adverse reaction within 7 days after vaccination
- Occurrence of adverse events (AEs) till Day 56
- Occurrence of serious adverse events (SAEs) till Day 56
- GMT of antigen-specific antibody (Anti-S1-RBD) on Day 14, 28, 42 and 56
- Seroconversion rate (SCR) of antigen-specific antibody on Day 14, 28, 42 and 56
- Geometric mean fold increase of antigen-specific antibody on Day 14, 28, 42 and 56
- GMT of neutralizing antibody against SARS-CoV-2 on Day 14, 28, 42 and 56
- SCR of neutralizing antibody against SARS-CoV-2 on Day 14, 28, 42 and 56
- Geometric mean fold increase of neutralizing antibody against SARS-CoV-2 on Day 14, 28, 42 and 56
- Correlation between the immune response detected by ELISA and live virus neutralization test
- Positive rate and level of antigen-specific interferon-gamma (IFN- γ) measured by ELISpot on Day 7, 28, and 35
- CD4⁺ and CD8⁺ T cell responses using intracellular cytokine staining and flow cytometry on Day 7, 28, and 35

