7.4.4 Contraindications to Second Vaccination

The following conditions constitute a contraindication to vaccination and should be checked prior to second vaccination:

1. Had any Grade 4 adverse reaction within 7 days after first dose.

-
2. Subject diagnosed with SARS-CoV-2 infection or has suspected SARS-CoV-2 infection based on symptoms according to investigator's judgment (lab test conformation is not necessary).
 3. Had any SAE related to first dose during the follow-up of first dose.
 4. Any condition that in the opinion of the investigator would be a contraindication to a second vaccination.
 5. Subject has a fever.
 6. Subject becomes pregnant.

If any AEs other than listed above or fever occurred at the time scheduled for vaccination, the subject may be vaccinated at a later date no later than 7 days when symptoms or fever were resolved.

Any subjects who receive the vaccination with dosage deviation or who does not receive the second vaccination on schedule may not necessarily be withdrawn from the study as further study procedures and the follow-up visits may be performed which will be decided by sponsor.

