10.2 Datasets or Populations Analysed

Safety Set

The Safety Set (SS) will consist of all subjects receiving at least one injection of the UB-612 vaccine. The Safety Set is for safety evaluation in analysis.

Full Analysis Set

The Full Analysis Set (FAS) will consist of subjects who receive two vaccinations, have at least one immunogenicity assessment after vaccination, and without SARS-CoV-2 infection between Day 0 and Day 56. Subject receive prohibited medication/treatment/vaccine during pre-specified period has impact on immunogenicity may exclude from the FAS set. The FAS set is the primary analysis set for immunogenicity evaluation.

Modified Intention-to-Treat Set

The modified intention-to-treat Set (mITT) will consist of subjects who receive at least one vaccination and have at least one immunogenicity assessment after the first or second vaccination. The mITT is also analysed for immunogenicity evaluation.

Per Protocol Set

The Per Protocol Set (PPS) will be a subset of FAS. PPS includes subjects who receive two vaccinations, have at least one immunogenicity assessment on Day 42 or 56 after vaccination, and without SARS-CoV-2 infection between Day 0 and Day 56. Subjects who had major protocol deviations as determined by the Study Team or who received prohibited medication/treatment/vaccine during the pre-specified period **leading to an impact on immunogenicity will be excluded from the PPS set**. The PPS is also analysed for immunogenicity evaluation as a sensitivity analysis.

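### V-122, Section 10.6: the two-dose completer population is applied to the interim safety endpoints, so subjects barred from dose 2 by a severe dose-1 event are left out of the interim rates

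*Supplement*

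**What the plan says.** All section numbers are those of the V-122 protocol unless another protocol is named.

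- **Interim population (10.6).** "Interim analysis population will be the subjects in groups A, B and C who had completed two vaccinations". The preceding sentence already fixes the timing (two-dose subjects in all three groups have reached Visit 9), so this one is a population rule.
- **Interim safety endpoints (10.6).** The same report lists "Occurrence of adverse reaction within 7 days after vaccination", AEs up to Day 56, and "Occurrence of serious adverse events (SAEs) till Day 56", alongside the antibody and T-cell endpoints.
- **Interim data sources (10.6).** The interim also takes in two administrative analyses of available data. The first covers Days 0 to 28 in Groups A, B and C. No two-dose condition is attached.
- **Bars to dose 2 (7.4.4).** These include "Had any Grade 4 adverse reaction within 7 days after first dose", "Had any SAE related to first dose during the follow-up of first dose" and "Any condition that in the opinion of the investigator would be a contraindication to a second vaccination". Known or suspected infection, fever and pregnancy are also listed.
- **Replacement (7.4.5.1).** A subject who stops vaccine because of an AE is not replaced.
- **Safety population (10.2).** "The Safety Set (SS) will consist of all subjects receiving at least one injection of the UB-612 vaccine". Its purpose is stated: "The Safety Set is for safety evaluation in analysis". Section 10.6 does not refer to it.
- **Primary endpoints (6.2).** There are two. The second, the percentage of subjects with a Grade 3 or higher AE within 7 days of vaccination, is not on the interim list.

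**The concern.** A safety analysis should not choose its subjects by their safety outcome. Receiving dose 2 depends in part on how dose 1 was tolerated, so a completer population conditions on the quantity being estimated. For two kinds of event, a Grade 4 reaction within 7 days of dose 1 and an SAE related to dose 1, the protocol itself turns the event into non-receipt of dose 2. Under the population sentence that subject then leaves both the numerator and the denominator.

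A two-dose requirement suits immunogenicity, and the FAS in 10.2 carries one. Section 10.6 extends that kind of restriction to safety without giving a reason. What is at stake is whether the interim safety tables give an undistorted account of first-dose tolerability in a first-in-human dose escalation, where one severe event among 20 subjects matters.

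**Working it through.** **1. The plan's own figure.** No stated figure depends on this rule. V-122 has no power calculation; 10.8 gives 20 per group, and 3 × 20 = 60, which agrees with the stated total. As a check on method, exact (Clopper-Pearson) limits reproduce those in Table 5-2 of the V-123 protocol: 18/20 gives 68.30% to 98.77%, 19/20 gives 75.13% to 99.87%, and 20/20 gives 83.16% to 100%.

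**2. Following one subject through the rules.**
- Grade 4 reaction or related SAE after dose 1: dose 2 is contraindicated (7.4.4).
- Vaccine stopped for an AE: no replacement (7.4.5.1), so the group's denominator falls from 20 to 19.
- Two vaccinations not completed: outside the interim population (10.6).
- At least one injection received: inside the Safety Set (10.2).

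The two sections therefore give different safety populations for the same subject.

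**3. Size, as an illustration.** The documents plan no rate for these events, so the number affected, k, is an assumption. The Safety Set gives k/20. The completer population gives 0/(20 − k), provided the contraindication is followed. The exact upper limit for zero events in n is 1 − 0.025^(1/n); for n = 19 this is 1 − 0.025^(1/19) = 17.65%.

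| Affected in a group of 20 (assumed) | Safety Set (exact 95% CI) | Two-dose completers (exact 95% CI) |
|---|---|---|
| 1 | 1/20 = 5.0% (0.13 to 24.87) | 0/19 = 0% (0 to 17.65) |
| 2 | 2/20 = 10.0% (1.23 to 31.70) | 0/18 = 0% (0 to 18.53) |
| 3 | 3/20 = 15.0% (3.21 to 37.89) | 0/17 = 0% (0 to 19.51) |

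Pooled over three groups, one affected subject changes 1/60 = 1.67% (0.04 to 8.94) to 0/59 = 0% (0 to 6.06).

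**4. How often the rule would bite.** The chance of at least one affected subject among 60 is 1 − (1 − p)^60. For assumed per-subject rates of 1%, 2% and 5% it is 45%, 70% and 95%.

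**5. Direction for other endpoints.** Subjects who miss dose 2 for unrelated reasons are also dropped. If such a subject had no event, the observed rate rises. For example, V-205 Section 5.4 reports adverse reactions after dose 1 in 13 of 20 subjects at 10 µg (65.0%); losing one reaction-free subject would give 13/19 = 68.4%. The downward bias therefore attaches to the events that bar dose 2, not to every interim safety rate.

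**6. Conflict within 10.6.** A severe dose-1 reaction falls in the Days 0 to 28 window of the first administrative analysis, which is to be carried into the interim. The population sentence would remove the same subject. The section does not say which prevails.

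**The case against.** Much of the case on the other side stands.

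- **The events are not hidden from oversight.** Under 9.6.7 one Grade 4 adverse reaction, or one SAE possibly associated with vaccination, halts dosing and convenes the DSMB. Escalation rests on DSMB review after all subjects in a group have completed Day 7 (7.1, 9.7). The final safety analysis uses the Safety Set. No trial safety decision is shown to depend on the interim population.
- **A reader might infer that the excluded subjects are exactly those with a Grade 4 reaction or related SAE.** They are not. Infection, pregnancy, investigator opinion and withdrawal before dose 2 lead to the same exclusion, and a Grade 3 reaction is not a listed bar.
- **A reader might infer that severe dose-1 events cannot appear in the interim report at all.** That is too strong, because the administrative-analysis data are to be included and 10.7 says all available data will be displayed and used. The text is contradictory rather than unambiguous.
- **A reader might infer that the bias always favours the vaccine.** It does so for the events that bar dose 2. Loss of event-free subjects pushes other rates up.
- **A reader might infer that later protocols drew their safety statements from this restricted population.** The documents do not show it. The safety summary in V-123 Section 5.5 uses a data cut of 2021-05-13, when 59 of 60 subjects had completed Day 196 procedures. V-205 Section 5.4 has Day 56 titers for only the first six subjects in Group C, and a table note in its Section 10.2.2 dates that position to 2021-01-12, before the interim defined in 10.6 could be complete.
- **The Grade 3 or higher endpoint is a small omission.** Its events fall within the adverse-reaction and AE endpoints already listed, and 10.4 tabulates severity. What is missing is the primary summary itself.

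None of this gives a reason for using completers for safety. It limits the consequence.

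**Conclusion.** The point holds as a fault in the written rule, of moderate weight. Section 10.6 makes inclusion in the interim safety tables depend partly on the safety outcome, contrary to the Safety Set in 10.2 and unreconciled with the administrative-analysis sentence in 10.6. The interim rate of Grade 4 reactions and related SAEs after dose 1 is biased downward: with one affected subject in a group of 20, from 5.0% (upper limit 24.9%) to 0% (upper limit 17.6%). This assumes that the population sentence governs and the contraindications are followed; the number affected is illustrative.

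The defect is confined to the interim report, and nothing suggests that it had an effect. V-123 Section 5.5 reports no SAE and shows 20 subjects per group at Days 42 and 56. V-205 Section 5.4 reports no Grade 3 or higher adverse reaction within 7 days of either dose. These later results do not make the rule sound, since a prespecified population is judged before the outcome is known.

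Omitting the second primary endpoint is a separate, minor gap. V-123 Section 5.5 reports Grade 3 or higher AEs after dose 1 in 2 subjects (10.0%) at 10 µg and 1 (5.0%) at 30 µg, all assessed as unrelated. A summary limited to related reactions would not show them. The documents do not show that the interim list caused any such omission.

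**What to change.** In Section 10.6 of V-122:

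1. Use the Safety Set (at least one injection) for every interim safety endpoint.
2. Keep two-dose completers, or the FAS, for the interim immunogenicity endpoints only.
3. Reconcile the population sentence with the sentence that brings in the administrative-analysis data, so that each endpoint has one stated population.
4. Add the percentage of subjects with Grade 3 or higher AEs within 7 days to the interim endpoint list.

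The contraindications in 7.4.4 need no change for this purpose. The cost is a reworded population statement and one added bullet. No new data, visits or subjects are needed, and the Safety Set is already defined in 10.2.

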10.7 Handling of Missing Data

All available data will be displayed and utilized in data analysis. No imputation will be considered for the missing observations.

10.8 Determination of Sample Size

No formal statistical sample size and power computations are performed since the objectives of the study are to assess the safety and immunogenicity of the study vaccine. The sample size of each vaccine dose group is 20. In this study, twenty subjects will be involved in each vaccine dose group. A total of 60 subjects will be recruited.

10.9 Protocol Deviations

Protocol deviations will be categorized into important and non-important items, and definitions will be illustrated in the protocol deviation handling plan (PDHD). Events that beyond the PDHD will discuss with sponsor to determine the categorization.

11 QUALITY ASSURANCE AND QUALITY CONTROL

11.1 Audit and Inspection

Study centers and study documentation may be subject to Quality Assurance audit during the course of the study by the sponsor or its nominated representative. In addition, inspections may be conducted by regulatory authorities at their discretion.

11.2 Monitoring

Data for each subject will be recorded on an eCRF. Data collection must be completed for each subject who signs an ICF and is administered study agent.

In accordance with current good clinical practice (cGCP) and International Council for Harmonisation (ICH) guidelines, the study monitor will carry out source document verification at regular intervals to ensure that the data collected in the eCRF are accurate and reliable.

The investigator must permit the monitor, the IEC/IRB, the sponsor's internal auditors, and representatives from regulatory authorities direct access to all study-related documents and pertinent hospital or medical records for confirmation of data contained within the eCRFs.

11.3 Data Management and Coding

The sponsor and/or the appointed representative(s) will be responsible for activities associated with the data management of this study. This will include setting up a relevant database and data transfer mechanisms, along with appropriate validation of data and resolution of queries. Data generated within this clinical study will be handled according to the relevant standard operating procedures of the data management and biostatistics departments of the sponsor and/or the appointed representative(s).

Study centers will complete the eCRF. Data entered into the eCRF must be verifiable against source documents at the study center. Data to be recorded directly on the eCRF will be identified and the eCRF will be considered the source document. Any changes to the data entered into the data capture system will be compliant to FDA CFR 21 Part 11.

Medical coding will use Medical Dictionary for Regulatory Activities for AEs.

Missing or inconsistent data will be queried to the investigator for clarification. Subsequent modifications to the database will be documented.

12 RECORDS AND SUPPLIES

12.1 Drug Accountability

On receipt of the study agent (including rescue medication, if relevant), the investigator (or designee) will conduct an inventory of the supplies and verify that study agent supplies are received intact and in the correct amounts before completing a supplies receipt. The investigator will retain a copy of this receipt at the study center and return the original receipt to the study monitor. The monitor may check the study supplies at each study center at any time during the study.

It is the responsibility of the study monitor to ensure that the investigator (or designee) has correctly documented the amount of the study agent received, dispensed, and returned on the dispensing log that will be provided. A full drug accountability log will be maintained at the study center at all times. The study monitor will arrange collection of unused study agent returned by the subject. The study monitor will also perform an inventory of study agent at the close-out visit to the study center. All discrepancies must be accounted for and documented.

12.2 Financing and Insurance

Financing and insurance of this study will be outlined in a separate agreement between the contract research organization and the sponsor.

13 ETHICS

13.1 Independent Ethics Committee or Institutional Review Board

Before initiation of the study at each study center, the protocol, the ICF, other written material given to the subjects, and any other relevant study documentation will be submitted to the appropriate IEC/IRB. Written approval of the study and all relevant study information must be obtained before the study center can be initiated or the study agent is released to the investigator. Any necessary extensions or renewals of IEC/IRB approval must be obtained for changes to the study such as amendments to the protocol, the ICF or other study documentation. The written approval of the IEC/IRB together with the approved ICF must be filed in the study files.

The investigator will report promptly to the IEC/IRB any new information that may adversely affect the safety of the subjects or the conduct of the study. The investigator will submit written summaries of the study status to the IEC/IRB as required. On completion of the study, the IEC/IRB will be notified that the study has ended.

13.2 Regulatory Authorities

Relevant study documentation will be submitted to the regulatory authorities of the participating countries, according to local/national requirements, for review and approval before the beginning of the study. On completion of the study, the regulatory authorities will be notified that the study has ended.

13.3 Ethical Conduct of the Study

The investigator(s) and all parties involved in this study should conduct the study in adherence to the ethical principles based on the Declaration of Helsinki, cGCP, ICH guidelines, and the applicable national and local laws and regulatory requirements.

13.4 Informed Consent

The process of obtaining informed consent must be in accordance with applicable regulatory requirement(s) and must adhere to cGCP.

The investigator is responsible for ensuring that no subject undergoes any study related examination or activity before that subject has given written informed consent to participate in the study.

The investigator or designated personnel will inform the subject of the objectives, methods, anticipated benefits and potential risks and inconveniences of the study. The subject should be given every opportunity to ask for clarification of any points s/he does not understand and, if necessary, ask for more information. At the end of the interview, the subject will be given ample time to consider the study. Subjects will be required to sign and date the ICF. After signatures are obtained, the ICF will be kept and archived by the investigator in the investigator's study file. A signed and dated copy of the subject ICF will be provided to the subject or their authorized representative.

It should be emphasized that the subject may refuse to enter the study or to withdraw from the study at any time, without consequences for their further care or penalty or loss of benefits to which the subject is otherwise entitled. Subjects who refuse to give or who withdraw written informed consent should not be included or continue in the study.

If new information becomes available that may be relevant to the subject's willingness to continue participation in the study, a new ICF will be approved by the IEC(s)/IRB(s) (and regulatory authorities, if required). The study subjects will be informed about this new information and re-consent will be obtained.

13.5 Subject Confidentiality

Monitors, auditors, and other authorized agents of the sponsor and/or its designee, the IEC(s)/IRB(s) approving this research, and the United States (US) FDA, as well as that of any other applicable agency(ies), will be granted direct access to the study subjects' original medical records for verification of clinical study procedures and/or data, without violating the confidentiality of the subjects to the extent permitted by the law and regulations. In any presentations of the results of this study or in publications, the subjects' identity will remain confidential.

All personal data collected and processed for the purposes of this study should be managed by the investigator and his/her staff with adequate precautions to ensure confidentiality of those data, applicable to national and/or local laws and regulations on personal data protection.

14 REPORTING AND PUBLICATION, INCLUDING ARCHIVING

Essential documents are those documents that individually and collectively permit evaluation of the study and quality of the data produced. After completion of the study (end of study defined as the date of the last visit of the last subject), all documents and data relating to the study will be kept in an orderly manner by the investigator in a secure study file. This file will be available for inspection by the sponsor or its representatives. Essential documents should be retained for 2 years after the final marketing approval in an ICH region or for at least 2 years since the discontinuation of clinical development of the investigational product. It is the responsibility of the sponsor to inform the study center when these documents no longer need to be retained. The investigator must contact the sponsor before destroying any study related documentation. In addition, all subject medical records and other source documentation will be kept for the maximum time permitted by the hospital, institution, or medical practice.

The sponsor must review and approve any results of the study or abstracts for professional meetings prepared by the investigator(s). Published data must not compromise the objectives of the study. Data from individual study centers in multicenter studies must not be published separately.

2 SYNOPSIS

Protocol Number:

V-123

Title:

A Phase I, Open-Label Extension Study to Evaluate the Safety, Tolerability, and Immunogenicity of UB-612 Vaccine in healthy adult volunteers

Investigational Product:

UB-612 vaccine

Phase:

Phase I extension study

Objectives:

Primary Objective:

- To evaluate the safety and tolerability of a booster dose of UB-612 vaccine in Phase I subjects.
- To evaluate the SARS-CoV-2 neutralizing antibody titers induced by a booster dose of UB-612.

Secondary Objective:

- To evaluate the humoral immune response to SARS-CoV-2 during this study.

Exploratory Objective:

- To evaluate the cellular immune response induced by **a booster dose of** UB-612.
- To evaluate the neutralizing antibody titer against SARS-CoV-2 variants induced by **a booster dose of** UB-612.
- **To compare primary series and booster vaccination of UB-612 on humoral immune responses**
- **To evaluate the kinetics of humoral immune responses of primary series and booster vaccination**
- **To evaluate the effect of prime-boost interval on immune responses**

Study Design:

This is an extension study to evaluate the safety, tolerability and immunogenicity of one booster dose of UB-612 COVID-19 vaccine in adults who completed two vaccinations of UB-612 vaccine 10, 30, and 100 µg in V-122 study (Phase I).

The subjects who completed two vaccinations in Phase I study will be recruited in this extension study. After the informed consent is obtained from the subject, eligible subjects will receive one booster dose of UB-612 vaccines 100 µg with the same dose which was offered in Phase II study, at least 6 months after **completing the 2-dose primary vaccination series..** This study will be carried out in three groups:

- (1) A group: 1 booster dose of UB-612 vaccine 100 µg, for subjects at UB-612 vaccine 10 µg group previously
- (2) B group: 1 booster dose of UB-612 vaccine 100 µg, for subjects at UB-612 vaccine 30 µg group previously
- (3) C group: 1 booster dose of UB-612 vaccine 100 µg, for subjects at UB-612 vaccine 100 µg group previously

In this study, there will be 3 clinical visits. Subjects will come to the clinics at Visit 1 (Day 1, baseline, booster vaccination, at least 6 months after **completing the 2-dose primary vaccination series** in V-122 study), Visit 2 (Day 15), and Visit 3 (Day 85, 3 months after booster vaccination).

In all groups, an informed consent and the eligibility of subjects will be checked at Visit 1 (Day 1). The booster study vaccine administration will be done immediately after blood draw which will evaluate baseline laboratory safety and humoral / cellular immune response/ SARS-CoV-2 test. All subjects in each group will be monitored at least 30 minutes after vaccination (for vital signs change and adverse events). The post-vaccination e-diary card for 7-day

solicited adverse events after vaccination will be given to subjects with a suitable instruction.

At Visit 2 (Day 15), subjects will return to clinics for laboratory safety check and have a blood drawn for humoral / cellular immune response.

At Visit 3 (Day 85, 3-month follow-up visit after booster vaccination), the subjects will return to clinics and have blood drawn for humoral immune / cellular immune response/ SARS-CoV-2 test.

All adverse events and serious adverse events will be monitored from Visit 1 (Day 1) until Visit 3 (Day 85).

Number of Subjects:

All subjects, up to 60 subjects, who completed two vaccinations in Phase I study will be enrolled into this extension study.

Treatment:

One 0.5 mL dose of UB-612 vaccines, 200 µg/mL, containing Adju-Phos® and CpG1, will be administered by an intramuscular (IM) injection **in the deltoid muscle** (on Day 1).

Duration of Treatment: 3 months

Study Population:

To be eligible for study entry, subjects must satisfy all of the following inclusion criteria:

1. Male or non-pregnant female who previously participated in and completed two vaccinations in the V-122 Study.
2. Women of childbearing potential and men must agree to practice medically effective contraception during study period. The acceptable effective contraception methods include:
 - a. Male or female sterilization, implant, or intrauterine device;
 - b. Injectable, pill, patch, ring plus one barrier method*;
 - c. Two combined barrier methods*.

*Effective barrier methods are diaphragm, male or female condoms, sponge, or spermicides (creams or gels that contain a chemical to kill sperm).

3. Able to understand the content and possible risks of informed consent and willing to sign the Informed Consent Form (ICF).
4. Able to understand and agrees to comply with all study procedures and be available for all study visits.
5. Ear temperature ≤ 38.0°C.
6. At screening visit, at least 6 months after **completing the 2-dose primary vaccination series** in the V-122 study.

Subjects will be excluded from the study if one or more of the following exclusion criteria is applicable:

1. Female who is pregnant or positive in pregnancy test at screening visit.
2. Female who is breast-feeding or plans to breastfeed within 90 days after booster vaccination.
3. Any acute illness, as determined by the study investigator 3 days before booster vaccination.
4. Prior administration of attenuated, nucleic acid (mRNA or DNA) or vectored vaccines in last 1 month before booster vaccination or expectation of such vaccines in the month after the booster vaccination.
5. Prior administration of subunit vaccine or inactivated vaccine in last 14 days before booster vaccination or expectation of receipt of such vaccines in the 14 days after the booster vaccination.
6. Any medical disease or condition that, in the opinion of the study investigator, may confound the results of the study or pose an additional risk to the subjects by their participation in the study.

7. Previous exposure to SARS-CoV-2 or receipt of an investigational or EUA vaccine product for the prevention of COVID-19, MERS or SARS, except UB-612.
8. Subjects who take part in another clinical study, other than V-122 study, within 12 weeks prior to the day of informed consent.
9. Prior administration of immunoglobulins and/or any blood products in last 4 months before booster vaccination.
10. Prior chronic administration (defined as ≥ 14 day of continuous use) of immunosuppressant or corticosteroids (equivalent to ≥ 20 mg daily of prednisone), cytotoxic treatment in last 6 months before booster vaccination.

Primary Endpoint(s):

Immunogenicity Endpoint(s)

- Geometric mean titer (GMT) of neutralizing antibody against SARS-CoV-2 (**Wuhan strain**) on Day 1, 15 and 85
- Geometric mean fold increase (**GMFI**) of neutralizing antibody against SARS-CoV-2 (**Wuhan strain**) on Day 15 and 85

Safety Endpoint(s)

- Occurrence of adverse reactions within 7 days after vaccination
- The percentage of subjects with \geq Grade 3 adverse events within 7 days after vaccination

Secondary Endpoint(s):

Immunogenicity Endpoint(s)

- GMT of antigen-specific antibody (Anti-S1-RBD) on Day 1, 15 and 85
- Geometric mean fold increase of antigen-specific antibody (Anti-S1-RBD) on Day 15 and 85
- Distribution of titers
- Correlation between the immune response detected by ELISA and live virus neutralization test

Safety Endpoint(s)

- Occurrence of serious adverse events during the whole follow-up period (3 months)
- Occurrence of adverse events of special interests (AESIs), medically attend adverse events (MAAEs) and serious adverse events (SAEs) during the study period
- Changes of safety laboratory measures

Exploratory Endpoint(s):

- T cell responses to UB-612 measured by ELISpot and flow cytometric assays on Day 1, 15 and 85
- GMT of neutralizing antibody against SARS-CoV-2 variants on Day 1, 15, 85 using pseudovirus neutralizing antibody assay
- **The comparison between primary series and booster vaccination on the humoral immune response by comparing the Day 15 GMT and GMFI of neutralizing antibody (Wuhan strain) and antigen-specific antibody (Anti-S1-RBD) after booster dose to the GMT and GMFI 2 weeks after the second dose of the primary vaccination series (i.e. Day 42 of V-122 Phase 1).**
- **The comparison between primary series and booster vaccination on the humoral immune response by comparing the Day 85 GMT and GMFI of neutralizing antibody (Wuhan strain) and antigen-specific antibody (Anti-S1-RBD) after booster dose to the GMT and GMFI 3 months after the second dose of the primary vaccination series (i.e. Day 112 of V-122 Phase 1).**
- **Figures (dot-plot) to show the individual responses and GMT of neutralizing antibody (Wuhan strain) and antigen-specific antibody (Anti-S1-RBD) at each time point of V-122 Phase 1 and V-123 Phase 1**

extension studies in order to provide a comprehensive view of the kinetics of the primary and booster immune responses.

- **Figures (dot-plot) of individual prime-boost interval with immune responses to show 1) individual fold increase of Day 15 value of neutralizing antibody (Wuhan strain) compared with baseline of V-122 Phase 1 study, 2) individual fold increase of Day 15 value of neutralizing antibody (Wuhan strain) compared with baseline of this V-123 study, 3) individual fold increase of Day 15 value of antigen-specific antibody (Anti-S1-RBD) compared with baseline of V-122 Phase 1 study, 4) individual fold increase of Day 15 value of antigen-specific antibody (Anti-S1-RBD) compared with baseline of this V-123 study, 5) individual ELISpot IFN-gamma on Day 15.**

Sample Size Determination

A total of 60 subjects who had enrolled in V-122 phase I Study will be recruited.

Statistical Analysis

The Safety Set (SS) will consist of all subjects who completed two vaccinations in Phase I study enrolled into this extension study and received one booster dose of UB-612 vaccines with the same dose as Phase II study. The Safety Set is for safety evaluation in analysis.

The Full Analysis Set (FAS) will consist of subjects who completed two vaccinations in Phase I study enrolled into this extension study, received one booster dose of UB-612 vaccines with the same dose as Phase II study, and have at least one immunogenicity assessment on Day 15 or 85 after vaccination. Subjects receive prohibited medication/treatment/vaccine during pre-specified period has impact on immunogenicity may exclude from the FAS set.

The Per Protocol Set (PPS) will be a subset of FAS. PPS includes subjects who completed two vaccinations in Phase I study enrolled into this extension study, received one booster dose of UB-612 vaccines with the same dose as Phase II study, and were compliant to the protocol. Subjects who had major protocol deviations as determined by the Study Team or who received prohibited medication/treatment/vaccine during the pre-specified period leading to an impact on immunogenicity will be excluded from the PPS set. The PPS is also analysed for immunogenicity evaluation.

All safety assessments, including AEs, PEs, VS, and clinical laboratory evaluations, where indicated, will be presented using descriptive statistics for each vaccine group of UB-612. Data will be summarized for each vaccine group.

All adverse reactions within 7 days after vaccination will be summarized with numbers and percentages by study vaccine groups. The percentage of subjects with \geq Grade 3 adverse events within 7 days after vaccination will also be demonstrated by study vaccine groups. AEs till Day 85 will be presented with number and percentage by system organ class, preferred term, and study vaccine groups. The number and percentage of SAEs during the whole follow-up period (3 months) will be presented in summary table by study vaccine groups. Adverse events of special interest during the study period will be summarized with number and percentage from the mapping result by MedDRA.

Changes of safety laboratory measures will be summarized with descriptive statistics by study vaccine group and each time point. ANCOVA model with laboratory baseline values as covariate will analyze changes of safety laboratory measures for testing the difference among vaccine groups. Pair-wise comparisons of least square means from the ANCOVA model will be presented. Intra-group difference in safety laboratory measures will also be analyzed by paired t test.

Geometric mean titer (GMT) will be described by descriptive statistics and the 95% confidence interval for study vaccine group. The difference on Day 1 among vaccine groups will be analyzed by ANOVA model under log-transform data. Additionally, the difference on Day 15 and 85 among vaccine groups will be analyzed by ANCOVA model under log-transform data with baseline level as covariate, if appropriate. Pair-wise comparisons of least square means from the ANOVA or ANCOVA model will be presented. The reverse cumulative distribution plot will be provided to display the distribution of titer by time points for each vaccine group.

Geometric mean fold increase (GMFI) in each study vaccine group is summarized by descriptive statistics and the 95% confidence interval for study vaccine group. The difference among vaccine groups will be analyzed by ANOVA. Pair-wise comparisons of least square means from the ANOVA model will be presented. The reverse cumulative distribution plot will be provided to display the distribution of fold increase by time points for each vaccine group.

For anti-S1-RBD ELISA, ACE2:RBD inhibition ELISA, and Neutralizing antibody titers, reverse cumulative distribution of titers and fold increases will be displayed at Day1, 15 and 85.

Neutralizing antibody GMT and GMFI will be determined against at least the following SARS-CoV-2 variants: Alpha (B.1.1.7), Beta (B.1.351), Gamma (P.1), and Delta (B.1.617.2). The fold decrease between titers of the original (Wuhan) strain and each variant will be determined, and compared using descriptive statistics.

